1.0 BACKGROUND, OBJECTIVE AND SPECIFIC AIMS

1.1.1 The Need for Novel Therapeutic Approaches for Depression

In this proposal, we aim to assess the efficacy and tolerability of Magnetic Seizure Therapy (MST) as an alternative to electroconvulsive therapy (ECT) for depression. Even with multiple medication trials, 30 - 40% of patients will experience a pharmacologically resistant form of illness [1]. In Canada, estimates have quantified the total mental health burden of MDD to be \$14.4 billion in 1998 (not accounting for decreased productivity associated with the illness estimated to be about \$6 billion [2]). The ineffectiveness of current treatments for major depressive disorder (MDD) coupled with the economic burden associated with the disorder engenders a need for novel therapeutic interventions that can provide greater response and remission rates.

The need to optimize our therapeutic approach to depression is twofold. First, while ECT is a well-established and highly effective treatment for depression with remission rates ranging from 60% to 80% [3], less than 1% of patients with treatment resistant depression (TRD) receive ECT in Canada and the United States [4, 5]. One of the major reasons that providers, patients and their families refuse to consider ECT - even when confronted with a disabling depression - is their concern about the cognitive side effects associated with ECT. The cognitive impairment includes anterograde and retrograde amnesia and prolonged post-treatment disorientation that is distressing to patients and mitigates the improvements in depressive symptomatology. MST offers a viable alternative to ECT with comparable response/remission rates and a more favourable cognitive adverse effect profile [6-8]. Second, it is vital to gain insight into the biological mechanisms underlying treatment response in order to better understand the physiological underpinnings of illness and treatment. To this end, we will evaluate the role of cortical inhibition (CI) from the dorsolateral prefrontal cortex as a biological target that can potentially predict MST and ECT treatment response. This will serve to deepen and enrich our biological models of depression, with the hope for more effective and personalized treatments.

1.1.2. Electroconvulsive Therapy (ECT) is Efficacious But Has Cognitive Adverse Effects

ECT is currently the most effective intervention for depression[9]. Despite evidence of significant efficacy (i.e., up to 75 percent remission rates in treatment resistant depression[9], ECT is complicated by its negative stigma and adverse cognitive effects. Regardless of treatment delivery, ECT results in significant post-ictal disorientation, and anterograde and retrograde amnesia[10]. Disorientation immediately after ECT can last up to 40 minutes, regardless of electrode placement[11], which lengthens the procedure and causes patients distress and burden[12]. Anterograde amnesia, the inability to learn and retain new information, can appear at the first ECT treatment [13, 14] and persist for up to several months [15-18]. Retrograde amnesia, the inability to recall past personal and impersonal memories, remains the most serious ECT cognitive adverse effect[19]. Retrograde amnesia is more severe with bilateral ECT (i.e., bifrontal or bitemporal) than right unilateral (RUL) ECT, with high compared to low dosages, and with brief pulse width relative to ultrabrief pulse width[10]. As recently highlighted by the US FDA, the extent of anterograde and retrograde amnesia, and the degree to which memory remains impaired post-ECT is a significant problem for patients and their families[20]. Numerous patients refuse ECT because of these adverse cognitive effects.

Several theories have been proposed to account for the adverse effects of ECT on memory. The most supported theory is that when an electrical seizure is initiated, the skull shunts electrical current away from the stimulation site. This electrical current is propagated throughout the brain by the corticospinal fluid (CSF) and ensures the electrical stimulus is non-focal[21, 22]. This diffuse electrical discharge spreads to deep brain regions, including medial temporal lobe structures (e.g., hippocampus) where it causes a disruption of synaptic plasticity and long-term potentiation[23], which are neural substrates of memory formation[24-27]. The development of a new treatment approach that can mitigate these adverse cognitive effects, following this theory of how ECT results in cognitive adverse effects while maintaining the robust efficacy of ECT, is needed.

The proposed study will employ a relatively new approach to delivering ECT through right unilateral electrode placement combined with ultrabrief pulse width (RUL-UB ECT; 0.3 msec). Animal and human studies have demonstrated that ultrabrief pulse widths induce more efficient seizures compared to standard pulse widths (0.5 to 1 msec)[28]. When applied at six times the seizure threshold, RUL-UB ECT was shown to be as effective as standard pulse width RUL ECT but with significantly fewer and more attenuated cognitive adverse effects[10]. Although RUL-UB ECT does seem to reduce cognitive adverse effects, a greater number of treatments are required to produce comparable therapeutic effects to standard pulse width ECT[29-31] with increased cognitive impairments emerging after more treatment. Thus, patients treated with RUL-UB ECT still experience significant memory impairment compared to baseline.

1.1.3. Magnetic Seizure Therapy (MST) is a New Convulsive Neuromodulation Therapy

MST is an alternative form of convulsive therapy, that like ECT, involves the induction of a seizure to achieve a therapeutic response[22]. However, the induction of a seizure occurs through the use of high frequency, rTMS rather than high frequency, repetitive transcranial electrical stimulation. With magnetic stimulation, a rapid, high intensity, time varying magnetic field is able to pass into the brain without resistance and stimulate neurons thereby limiting seizure spread as the induced magnetic field can be focally targeted based on geometry of the stimulating magnetic coil[32, 33]. Additionally, the magnetic field is not impeded nor shunted by non-conducting material (i.e., skull) and, therefore, the field results in focal brain activation[34, 35]. Specifically, compared to right unilateral ultrabrief pulse ECT (RUL-UB-ECT), the electric field induced by MST is 5–10 times more focal[35, 36].

In an early study, White et al. compared 20 patients with severe depression openly allocated to receive ECT or MST. In the MST relative to the ECT group, time to orientation was much shorter (4 vs. 18 minutes, $p < 0.01$). The Hamilton Rating Scale for Depression-24 item (HRSD-24) score improved from 32 to 14 in the MST group, while in the ECT group the score improved from 30 to 6[37]. In another study, 20 TRD patients were allocated to receive either right unilateral (RUL) ECT or MST. Comparable antidepressant response and no cognitive side effects were observed in both groups[8]. Note that in the latter study, RUL ECT was administered at 3 times the seizure threshold, which reduced the cognitive side effects, but might hinder the response to ECT. A subsequent MST study done by the same group collated the data from the former study with 16

additional MST subjects. Remission was achieved by 46% of the patients, and no cognitive side effects were observed. FDG-PET scans (N=12) showed increased bilateral metabolic activity in the frontal cortex and decreased activity in the left striatum[38]. Based on theoretical calculations, Lee et al. found the electrical field to be 3-11 times stronger and the stimulated brain volume much larger (47-100% vs 21%) in ECT compared to MST. The improved focality and lower intensity of MST was suggested as a possible explanation for its favorable side effects profile[36]. In a within subject, non-human primate study, [name] et al. (collaborator, UT Southwestern) compared the effects of electroconvulsive seizure (ECS), magnetic seizure (MS), and anesthesia alone on a measure of spatial working memory. ECS resulted in lower correlation between predicted and actual response patterns in 2 of 3 subjects, which suggested impaired planning ability. In all 3 subjects, reaction time was significantly longer in ECS relative to MS and sham[39]. This preclinical study further substantiates the cognitive superiority of MST.

1.2.1 Neurophysiological Targets of Suicidal Ideation in TRD

The NIMH Research Domain Criteria (RDoC) proposes to use symptom clusters that cut across neuropsychiatric diagnoses as opposed to strict diagnostic classifications that have often failed to adequately capture recent advances in our understanding of the pathophysiology of severe psychiatric disorders[40]. To this end, several symptom constructs have been put forward to identify the depressive phenotype that is most closely associated with its underlying mechanism[41]. Suicidal ideation is a construct that is not part of the current RDoC matrix, but rather a construct that has been linked to maladaptive behaviors including hopelessness[42, 43], negative affect, and attentional biases[44]. These maladaptive behaviors are in the RDoC negative valence domain, specifically the RDoC constructs of loss, sustained threat, and frustrative non-reward[40]. Suicidal ideation has been posited to be a construct that shows heritability, state independence, and biological/clinical face validity[45]. It has been suggested that suicidal ideation may be more responsive to ECT than depressive symptoms[46, 47] and ECT is used as a first line treatment in TRD patients with significant suicidal ideation[46]. Therefore, suicidal ideation represents a symptom construct that is of major public health concern and associated with the TRD phenotype.

From a mechanistic viewpoint, suicidal ideation has been linked to the γ -aminobutyric acid (GABA)ergic system. Indeed, previous studies found abnormal GABA neurotransmission in suicidal patients, particularly in those with depression[48, 49]. Merali et al.[50] found that frontal mRNA expression of the GABA_A subunit, was reduced in depressed suicide victims compared to controls. Poulter et al.[51] reported that there was dysfunctional DNA methylation in the GABA_A receptor α 1 subunit promoter region which was under expressed in MDD suicide brains compared to patients who did not die as a result of suicide. Moreover, relative to non-depressed suicide patients, mRNA expression of several genes related to the GABA_A receptor is increased in depressed suicide patients[52]. It stands to reason that neurophysiological measures that assess GABAergic neurotransmission, such as integrated transcranial magnetic stimulation (TMS) and electroencephalography (EEG; TMS-EEG) can represent an important neurophysiological target. Conceptually, reduced GABAergic inhibitory neurotransmission may result in lack of control over one's own thoughts, which can become ruminative, persistent, and translate in a desire to die. This may explain our group's previous findings that relative to non-TRD patients, TRD was

associated with greater deficits in cortical inhibition (CI)[53], which is mediated by GABA inhibitory interneurons. In summary, for the treatment of suicidal ideation, evidence suggests that prefrontal GABAergic inhibitory neurotransmission may represent an important neurophysiological target.

1.3.1 Innovation

Several important areas of innovation are included in this study. We will conduct a randomized non-inferiority clinical trial designed to compare the efficacy of MST with ECT in patients with TRD. Suicidal ideation – a symptom domain in TRD that has tremendous public health impact - will be evaluated as the primary outcome variable of interest. In this study, we will follow an experimental medicine approach and evaluate CI as a potential mechanism through which MST and ECT may result in attenuation of suicidal ideation. Specific innovations include: 1) use of a new convulsive therapy, MST, 2) state-of-the-art combined TMS with EEG and analytic methods used to identify a neurophysiological GABAergic signal, and 3) use of quantitative EEG to probe mechanisms of ECT-induced cognitive impairment.

1.3.2 Pilot Data Support Innovative Study Methodology and Feasibility: Transcranial Magnetic Stimulation Measurement of CI in TRD

TMS can provide an index of GABA receptor-mediated inhibition in the cortex because it differentially stimulates inhibitory interneurons and pyramidal neurons. We have demonstrated TMS paradigms that provide a measure of GABA receptor-mediated inhibitory neurotransmission including the cortical silent period (CSP) and long interval cortical inhibition (LICI)[54-57]. The CSP relies on motor cortical stimulation superimposed on background electromyography (EMG) activity. At high stimulus intensities, a cessation of all EMG activity occurs (thus the ‘silent’ period). The duration of this ‘silent’ period provides a metric of GABAergic inhibition in the motor cortex[58]. LICI involves a suprathreshold conditioning stimulus (CS) preceding a suprathreshold test stimulus (TS) by 50-200 ms, resulting in recruitment of inhibitory interneurons and inhibition of the motor evoked potential (MEP) by 50 % [54].

Evidence suggest that LICI and CSP are mediated by cortical GABA_B interneurons[54, 55, 57, 59]. We have demonstrated evidence for deficient CI in patients with MDD and Bipolar Disorder using the above TMS inhibitory paradigms[53, 60]. Levinson et al.[53] found that all patients with MDD demonstrated significant CSP deficits. However, these studies were limited as measurement of CI was confined to the motor cortex and recorded in hand muscles through EMG. This limitation is problematic as the motor cortex has not been traditionally viewed as a key brain structure underlying the pathophysiology of MDD.

1.3.3 Recording CI from the dorsolateral prefrontal cortex (DLPFC) Using TMS-EEG. TMS-EEG is a powerful method to assess CI, excitability, connectivity and plasticity in non-motor cortical regions. Single and paired pulse TMS-EEG studies have identified several TMS-EEG indices associated with cortical inhibitory mechanisms associated with GABAergic neurotransmission[61-65]. In TMS-EEG, the application of single TMS pulse to the motor and prefrontal cortices results in generation of a series of TMS-induced cortical evoked potentials within the first 300 ms of the TMS pulse that results in descending corticospinal volleys and a

MEP. A series of studies including pharmacological probing and simultaneous recording of EEG and EMG response at the periphery have associated the N100 components with GABA_B receptor mediated inhibitory mechanisms [61-65]. In addition, we have previously reported LICl can be generated from the DLPFC[62] and both N100 and LICl have high test-retest reliability[66, 67].

1.3.4 Predicting Remission of Suicidal Ideation

Baseline Prediction: In relation to target engagement, we used TMS-EEG to identify the neurophysiological predictors of decreased suicidal ideation associated with MST treatment[68]. We applied single and paired pulse TMS-EEG to the left DLPFC at baseline prior to MST treatment in 27 TRD patients. Our recently published study[68]demonstrated that the amplitude of the N100 and the extent of LICl in frontal and central midline region significantly correlated with remission of suicidal ideation based on the Scale for Suicidal Ideation[69]. This relationship was specific to the DLPFC and was not observed when N100 and LICl were assessed in the motor cortex. Additionally, we demonstrated that N100 and LICl in the frontal cortex predicted remission of suicidal ideation with 90% sensitivity and 89% specificity[68].

Target engagement: LICl was derived from the left DLPFC in 20 TRD patients prior to and after a course of MST treatment. Change in LICl predicted remission of suicidal ideation correctly with 85.7% sensitivity and 100% specificity (AUC = 0.98, p = 0.002). This pilot data suggests that LICl is modified by MST and that individualized changes in LICl by MST may underlie the differential treatment response for suicidal ideation.

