3.0 OBJECTIVES AND HYPOTHESES

Primary objective: To assess the efficacy and cognitive adverse effects of MST compared to RUL-UB ECT in patients with depression.

Primary hypothesis/combined effectiveness endpoint: (1) MST will result in remission rates on the 24-item Hamilton Rating Scale for Depression (HRSD-24) that is non-inferior to that of RUL-UB ECT; **AND** (2) MST will have a superior cognitive adverse effect and tolerability profile compared to RUL-UB ECT as assessed with the Autobiographical Memory Test (AMT).

Secondary objective: To assess the efficacy MST compared to RUL-UB ECT in ameliorating suicidal ideation in patients with depression.

Secondary hypothesis/effectiveness endpoint: MST will have a non-inferior remission rate on the SSI compared to RUL-UB-ECT in patients with depression.

Tertiary objective: To refine and develop candidate neurophysiological biomarker, cortical inhibition (CI), using combined transcranial magnetic stimulation and electroencephalography (TMS-EEG) that may predict response to treatment using remission of suicidal ideation as a meaningful clinical indicator.

Tertiary hypothesis/effectiveness endpoint: (1) Change in CI in the DLPFC following MST will significantly predict SSI reduction; (2) Following MST and ECT, increased complexity in course time scales derived through multi-scale entropy will be associated with change in the AMT scores in patients with depression.

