5.8.4 Tertiary Outcome Analysis: Neurophysiological Data

We will investigate the relationship between change in CI and SSI reduction by calculating the area under the receiver operating characteristic (ROC) curve (AUC) as discussed above (Section 1.3.4). ROC analysis is used in medicine to evaluate diagnostic test accuracy. The ROC involves plotting the sensitivity (true positive rate) versus 1-specificity (false positive rate). The ROC AUC predicts performance of the diagnostic test. An AUC of 1 represents perfect prediction with optimal sensitivity and specificity while 0.5 suggests that the diagnostic test is no better than chance at diagnostic prediction. For our purposes, the ROC AUC then corresponds to the change in CI that optimally distinguishes MST and ECT remitters from non-remitters (defined as a zero score on the SSI). Based on our preliminary data described above (Section 1.3.4), we will use change in CI (defined as the LICl TMS-EEG response) to distinguish MST and ECT SSI remitters from non-remitters using a ROC AUC of >0.85 on all frontal electrodes using a false detection rate correction that is applied to all frontal electrodes.

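### The planned ROC of LICI change addresses prediction of SSI remission but cannot by itself support the protocol's mechanism wording; an arm comparison and a baseline LICI term would help

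*Combined protocol and SAP*

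**What the plan says.** - **Mechanism.** Section 1.3.1 says the trial will "evaluate CI as a potential mechanism through which MST and ECT may result in attenuation of suicidal ideation".
- **Pilot, baseline.** Section 1.3.4 describes TMS-EEG "at baseline prior to MST treatment in 27 TRD patients" and reports that the N100 amplitude and "the extent of LICl in frontal and central midline region significantly correlated with remission of suicidal ideation". Sensitivity was 90% and specificity 89%, given for N100 and LICI together.
- **Pilot, change.** In 20 patients, all treated with MST, change in LICI predicted SSI remission with sensitivity 85.7%, specificity 100%, AUC 0.98 and p = 0.002. The section labels this target engagement and concludes: "This pilot data suggests that LICl is modified by MST". It gives no mean change and no interval.
- **Formal objective.** Section 3.0 seeks a biomarker "that may predict response to treatment using remission of suicidal ideation as a meaningful clinical indicator". The hypothesis is: "Change in CI in the DLPFC following MST will significantly predict SSI reduction".
- **Data.** Section 5.3 and Table 1 have TMS-EEG recorded before and after the course in both arms. Section 5.3 calls N100 and LICI dependent variables but gives no model for them.
- **Analysis.** Section 5.8.4: "We will investigate the relationship between change in CI and SSI reduction by calculating the area under" the ROC curve, for SSI remitters against non-remitters in MST and ECT. The criterion is AUC >0.85 on frontal electrodes with a multiplicity correction. No formula for change, baseline term or arm comparison is given.

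**The concern.** Two questions are answered by one statistic. Whether LICI change separates remitters from non-remitters is a question of discrimination, and an ROC answers it. Whether treatment alters LICI, and whether MST and ECT alter it differently, is a question of mean change, and the ROC is silent on it. The pilot section already moves from the first to the second, and the trial would have only the same kind of evidence for its mechanism statement.

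A further ambiguity lies within the ROC. A post-minus-baseline score contains the baseline value. If baseline LICI predicts remission, as the pilot reports, part of the discrimination credited to change may come from where patients started.

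At stake is the wording that a tertiary result can bear. Neither the primary nor the secondary conclusion is affected.

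**Working it through.** **1. The pilot figure.** No sample size, power or alpha is stated for the LICI analysis, so only the pilot result can be checked. In 20 patients, 85.7% and 100% fit 6/7 with 13/13, or 12/14 with 6/6. The nearest attainable AUCs are 89/91 = 0.978 and 82/84 = 0.976, so 0.98 is consistent. A Mann-Whitney test gives p = 0.0001 to 0.0002 (exact) or 0.0006 to 0.0011 (normal), against the stated 0.002. The test used is not named, and nothing below depends on it.

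**2. The AUC does not depend on mean change.** It is the probability that a random remitter's change ranks above a random non-remitter's. Adding a constant to every change leaves the ranks alone.

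- With two normal groups 1.5 SD apart, mean change set to -1, 0 or +1 SD gives AUC 0.854 each time.
- For AUC 0.98 the separation is √2 × z(0.98) = 2.90 SD. With 35% remitters (assumed), group means of 0.65 × 2.904 = +1.89 and -0.35 × 2.904 = -1.02 average to zero.

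So even the pilot's AUC is compatible with no average change. This step needs no assumption about the trial's data.

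**3. Baseline carry-over.** Assumptions, none given in the documents:

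- change is post minus baseline;
- baseline LICI is standard normal, with remission following a logistic model in baseline tuned to AUC 0.90;
- the remission rate is 40% or 60%;
- post = ρ × baseline + √(1 - ρ²) × noise, so post adds nothing once baseline is known;
- 50 remitters and 50 non-remitters, one electrode.

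AUCs come from 400,000 simulated patients. The chance of significance uses Φ((AUC - 0.5)/SE - 1.96) with the Hanley-McNeil SE. The last column uses 4,000 samples per remission rate.

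| ρ | AUC of change, as computed | AUC, reversed | Significant against 0.5 | AUC >0.85 |
|---|---|---|---|---|
| 0.2 | 0.26 | 0.74 | over 99% | about 1% |
| 0.4 | 0.29 | 0.71 | 98% | under 0.2% |
| 0.6 | 0.33 | 0.67 | 88% | none |
| 0.8 | 0.38 | 0.62 | 57% | none |

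The direction is reversed: patients whose baseline was on the remitter side move the other way.

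**4. Sensitivity to baseline accuracy.** In a binormal model, with ρ the within-group pre-post correlation, the reversed AUC of change is Φ(d√(1 - ρ)/2), where d = z(sensitivity) + z(specificity).

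- Taking 90%/89% as if it held for LICI alone (an upper-end case): d = 2.51, baseline AUC 0.96. Change AUC is 0.90, 0.85, 0.81, 0.75, 0.71 and 0.65 at ρ = 0, 0.3, 0.5, 0.7, 0.8 and 0.9. It exceeds 0.85 only for ρ below 1 - (2 × 1.036/2.508)² = 0.32.
- With 75%/75%: d = 1.35, and change AUC runs from 0.75 (ρ = 0) to 0.58 (ρ = 0.9).
- If the baseline difference is a stable trait still present after treatment, the AUC is 0.50.

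**5. Effect of adjustment.** In the upper-end case with no true effect of change (N = 100 or 260, ρ = 0.5 to 0.9, 60% remission), the unadjusted test rejects in 76 to 100% of simulations. With baseline LICI in the model, change is significant in 3 to 6%.

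**The case against.** The strongest reply is that the plan does what it formally sets out to do. Aim 3 in 1.4.1 and the objective and hypothesis in 3.0 concern prediction, and target engagement is named only in the pilot description. A reader might infer that the trial fails to test a stated engagement objective; the documents do not support that. The mechanism statement in 1.3.1 remains, and the ROC cannot carry it.

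A reader might also infer that carry-over would produce a false success. Against the >0.85 criterion it would rarely do so, especially at the high test-retest reliability asserted in 1.3.3, and its reversed direction could be seen once the sign of change is defined. What stands is narrower: the hypothesis in 3.0 speaks of significant prediction, and AUCs of this size often reach significance.

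It is tempting to add treatment resistance as a common cause, since 1.2.1 describes resistance as "associated with greater deficits in cortical inhibition (CI)[53], which is mediated by GABA inhibitory interneurons". But 1.3.2 says that work was confined to the motor cortex, 1.3.4 found the remission relationship only in the DLPFC, and the failed-trials covariate in 5.8.1 is listed for HRSD-24 remission. The chain is not established.

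Nor should a non-zero mean change be required. The pilot section proposes individualized changes behind differential response. Remitters rising while non-remitters fall would fit that with a mean of zero.

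**Conclusion.** The gap is real but modest. As planned, 5.8.4 can support a statement that LICI change discriminates SSI remitters. It cannot support a statement that MST or ECT modifies LICI, or that the two differ in this. That part follows from the definition of the AUC.

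Baseline carry-over is possible, not shown. Its size, AUC 0.74 to 0.62 in the reverse direction, rests on the assumed baseline AUC of 0.90, the correlations of 0.2 to 0.8, the change formula, and post-treatment LICI being uninformative given baseline. It could range from nothing (a persistent trait difference) to about 0.90 (the upper-end baseline accuracy with zero correlation).

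The recordings needed are already planned, so this is a gap in the analysis text and not in the design. For a tertiary analysis it is a cheap improvement to consider.

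**What to change.** In 5.8.4:

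- **(a) Add an ANCOVA** of post-treatment LICI on arm and baseline LICI. Report the change within each arm and the MST-ECT difference, with 95% confidence intervals. State that, without an untreated arm, within-arm change cannot be separated from time.
- **(b) Keep the ROC and add a logistic model** of SSI remission with baseline LICI and post-treatment LICI (or change) as separate terms. Beside baseline, either choice gives the same fit. Report the gain in AUC over baseline LICI alone, with a bootstrap confidence interval.
- **(c) Define change** by formula and sign, and rest any mechanism wording on (a) and (b), not on the raw AUC.

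The number with paired recordings is not stated, and 5.5 lets patients remain in the trial without biomarker testing. With an assumed pre-post correlation of 0.7, the half-width of the arm comparison is 1.96 × √((2/n)(1 - 0.49)): about 0.17 SD at 130 per arm, 0.25 SD at 65 and 0.31 SD at 40.

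The cost is a few lines of SAP text and a few extra models. The downside is that the AUC attributable to LICI change may be smaller than the raw one.
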